### 3.2 STUDY FLOWCHART

### 3.3 STUDY MATRIX

Time	At the time of the x-ray exam
Measurement of AP abdomen depth	x

### 4. STUDY POPULATION

#### 4.1 NUMBER OF PARTICIPANTS

As this is a pilot study, 20 patients will be required after any drop outs. This will be enough as an initial cohort to determine whether the computational model is accurate enough to merit

further clinical investigation, or if it is in need of adjustment. It would be prudent to aim for an even male/female split.

As there is no patient follow-up, the patient's trial recruitment ends when they leave the Radiology department having had their abdomen x-ray examination.

If any participant chooses to withdraw from the study after their x-ray examination, their data will be deleted from the study database. These participants will be replaced to ensure 20 participants overall.

#### **4.2 INCLUSION CRITERIA**

Any ambulatory patient attending Ninewells Hospital's Radiology department for an AP abdomen x-ray who does not have contrast media present.

Patients must be over 16 years old.

#### **4.3 EXCLUSION CRITERIA**

Patient's presenting with severe abdominal pain at the time of their examination, patients who have had contrast media injected within the last 24 hours and patients who are unable to give their consent.

### **5. PARTICIPANT SELECTION AND ENROLMENT**

#### **5.1 IDENTIFYING PARTICIPANTS**

Willing volunteers will be found from patients who have been referred for an AP abdomen x-ray examination in the Radiology department at Ninewells Hospital. When the patient reports to main reception, if their attendance is for an AP abdomen x-ray the receptionist will give them the PIS and a reply slip that should be completed if they wish to take part in the study after having read the PIS given back to the receptionist. The receptionist will then pass a reply slip to the PI who will be in the radiology department.

#### **5.2 CONSENTING PARTICIPANTS**

When it is time for the volunteer's examination, a radiographer will collect them from the waiting area as normal and bring them to the x-ray room as normal. Their examination will be performed on the Fuji Digital Radiography mobile x-ray machine in room D of main radiology at Ninewells Hospital. In the privacy of the x-ray room, the PI will answer any questions relating to the study and consent the patient,

Although there isn't much time between the patient receiving the PIS and being consented (a minimum of half an hour), the PIS for this study is not lengthy or complex and the details of what the study entails are not difficult to explain or understand. The patient's only interaction with the PI is at the time of their AP abdomen examination. For all of these reasons, it is felt that the reduced time period between the patient being given the PIS and being consented is appropriate and that it will not impact upon the patient's ability to give informed consent.

In addition, since the patients who attend for AP abdomen x-ray examinations at Ninewells Hospital are referred from all over the Hospital and the wider Dundee area, there is no controlled means of delivering the PIS to the patient at any prior stage.

This is proportionate and commensurate with the research being undertaken

Where a participant requests to speak with a physician from the study team the consent process will not be completed until the participant has spoken to the physician and had all their questions answered to their satisfaction.

The informed consent process will be conducted in compliance with TASC SOP07: Obtaining Informed Consent from Potential Participants in Clinical Research.

### **5.3 SCREENING FOR ELIGIBILITY**

Any patient who is undergoing an AP Abdomen x-ray examination in the main radiology department at Ninewells Hospital is eligible to participate as long as they are not in acute abdominal pain at the time of the examination and have not had an injection of contrast media within the previous 24 hours.

### **5.4 INELIGIBLE AND NON-RECRUITED PARTICIPANTS**

Patients who are in acute abdominal pain, who have had an injection of contrast media within the previous 24 hours or who decline to take part in the study will have their AP Abdomen x-ray examination as normal with no involvement from the principal investigator.

#### **5.4.1 Withdrawal procedures**

Study recruitment only lasts as long as it takes to perform an AP Abdomen x-ray examination; withdrawal will not be necessary for any patient.

If a patient were to change their mind about participation after their examination, their study data will be removed from the anonymised research database.

## **6. STUDY & SAFETY ASSESSMENTS**

There are no specific safety assessments necessary for participation in this study; the measurement of AP abdomen depth does not pose any risk and the patient will simply undergo an AP Abdomen x-ray examination as per their referral.

## **7. DATA COLLECTION & MANAGEMENT**

### **7.1 DATA COLLECTION**

The patient's sex and clinical indication (i.e. the reason given for the AP abdomen x-ray examination on the request) will be recorded along with the physical measurement of their AP abdomen depth.

These 3 variables will be recorded at the time of the x-ray examination by the principal investigator on the patient study form. The patient's x-ray image will be taken directly from the x-ray equipment by the principal investigator; the image is anonymised during this transfer process.

### **7.2 DATA MANAGEMENT SYSTEM**

As there is no complex analyses necessary, the anonymised data will be stored on a Microsoft Excel spreadsheet on an NHS Tayside computer.

Data management will be conducted in compliance with TASC SOPs on Data Management, including TASC SOP53 Data Management Systems in Clinical Research and TASC SOP48 Data Management in CTIMPs using Excel.

The data management system (DMS) will be Excel as approved by Sponsor. The DMS will be based on the protocol and Participant Study Form for the study and individual requirements of the investigators. The Participants Study Form will collect only information that is required to meet the aims of the study and to ensure the eligibility and safety of the participant. The study database will be compliant with TASC SOP53.

The database is managed in line with all applicable principles of medical confidentiality and UK law on data protection, namely, the Data Protection Act 1998, which brought UK law into line with the EU Data Protection Directive. The Data Controller will be the NHS Tayside and the Data Custodian will be the PI.

The CI may delegate Participant Study Form completion but is responsible for completeness, plausibility and consistency of the Participant Study Form. Any queries will be resolved by the CI or delegated member of the study team.

Database lock will be conducted in compliance with TASC SOP32 Locking Clinical Study Databases

## **8. STATISTICS AND DATA ANALYSIS**

### **8.1 SAMPLE SIZE CALCULATION**

The sample size for this pilot study will be 20 patients. There is no statistical aim or calculation in deriving this number; 20 is simply a high enough number as to allow for confidence in the computational model where all or most results are found to be individually accurate.

### **8.2 PROPOSED ANALYSES**

Analyses is straightforward; the difference between the computationally predicted AP abdomen depth and that measured for each individual participant will be expressed as a percentage. Some statistical analyses will be undertaken on the 20 individual results (average, median, minimum and maximum deviations). A t-test will be used to compare predicted and measured results.

All analyses will be undertaken by the principal investigator using Microsoft Excel and IBM SPSS.

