## **2.1.2 Secondary Objectives**

Any systematic inaccuracy found in the study could be used to further improve the values used in the computational model.

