### **2.2.2 Secondary Outcomes**

Any identified systematic inaccuracy could be used to further improve the values used in the computational model.

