[figure not shown]
The anonymised patient's x-ray image will be removed directly from the x-ray equipment using an NHS password protected USB memory stick. During this transfer, the software on the x-ray equipment will anonymise the image. This process has been checked using test

patients – the anonymisation process is complete – no patient identifiable information will be left on the image or within the electronic header.

The image will be transferred from the USB memory stick to an NHS Tayside password protected computer. From there, the necessary measurements will be made to allow the computational model to be used to estimate the patient's AP abdomen depth. This estimate will be compared to the physical measurement of AP abdomen depth made for the corresponding patient as recorded on the patient study form – this will determine the accuracy of the estimate.

There is no need for any patient follow up. Individual patients will only participate in the trial once. As this is a pilot study, 20 patients will be recruited in total. This will be enough as an initial cohort to determine whether the computational model is accurate enough to merit further clinical investigation, or if it is in need of adjustment.

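### No analysis in section 8.2 directly examines whether the model's error varies with patient depth, so a depth-related error could go unrecognised or appear only as a mean bias

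*Combined protocol and SAP*

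**What the plan says.** Section 8.2 expresses each patient's difference between predicted and measured depth as a percentage. It continues: "Some statistical analyses will be undertaken on the 20 individual results (average, median, minimum and maximum deviations". It then adds: "A t-test will be used to compare predicted and measured results". It does not say whether the test is paired or which depth is the denominator of the percentage.

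The secondary objective (2.1.2) reads: "Any systematic inaccuracy found in the study could be used to further improve the values used in the computational model". The secondary outcome (2.2.2) says nearly the same: "Any identified systematic inaccuracy could be used to further improve the values used in the computational model". Section 3.1 describes the decision the pilot should support as whether the model is "accurate enough to merit further clinical investigation, or if it is in need of adjustment", and section 4.1 repeats it. Section 8.1 rests the sample size of 20 on confidence in the model "where all or most results are found to be individually accurate", with no calculation.

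The data are paired by patient. Section 3.1 says: "This estimate will be compared to the physical measurement of AP abdomen depth made for the corresponding patient". Section 7.1 lists sex, clinical indication and measured depth, and says: "These 3 variables will be recorded at the time of the x-ray examination".

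**The concern.** An error in a depth estimate can be systematic in more than one way. It can be a constant offset, or it can change with depth, for example reading high in thin patients and low in thick ones. The two call for different adjustments. Section 8.2 is the only place that lists analyses. It names no plot, correlation, regression, limits-of-agreement analysis or depth-stratified summary, and no other section supplies one.

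At stake is the step after the pilot. If the error changes sign within the cohort, the mean can be close to zero and the t-test unremarkable. If it does not change sign, the t-test may reject, but the team learns only that there is a bias on average. In both cases the adjustment that the protocol foresees would lack a description of what to adjust for.

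**Working it through.** **Inputs.** From the documents: n=20 (8.1), and the four summaries and the t-test (8.2). Section 8.1 states that 20 has no statistical derivation, so there is no figure of the plan's own to reproduce. The documents give no depth distribution and no error size. Assumed throughout: depth mean 22 cm and SD 4 cm, scatter of the model's error (noise) SD 1 or 2 cm, two-sided 5% tests. Percentages are taken as signed and relative to measured depth.

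**1. What the summaries depend on.** The average, median, minimum and maximum are functions of the 20 percentages alone. Reassigning the same percentages to other patients changes none of them. The t-test concerns the mean difference.

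**2. Worked example (invented data).** Depths are 22 + 4 × normal quantile((i - 0.5)/20), i = 1 to 20, giving 14.2 to 29.8 cm. Set A has equally spaced deviations from +12% in the thinnest patient to -12% in the thickest. Set B has the same 20 values shuffled; from thinnest to thickest they are -6.9, 8.2, 0.6, 12.0, 9.5, -5.7, -9.5, -3.2, -8.2, 5.7, 6.9, -4.4, 3.2, -10.7, -0.6, -12.0, 4.4, -1.9, 10.7, 1.9.

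| | Set A | Set B |
|---|---|---|
| Average / median | 0% / 0% | 0% / 0% |
| Minimum / maximum | -12% / +12% | -12% / +12% |
| Mean difference | -0.28 cm | 0.00 cm |
| Paired t-test p | 0.47 | 1.00 |
| Unpaired t-test p | 0.79 | 1.00 |
| Slope of difference on depth, cm per cm (95% CI) | -0.41 (-0.46 to -0.36) | +0.01 (-0.19 to +0.22) |

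**3. How often the t-test would react.** Simulation, 20,000 runs per setting: predicted = depth + slope × (depth - c) + noise, where c is the depth at which the systematic error is zero; measured depth without reading error.

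| Paired t-test, slope -0.3 | Noise 1 cm | Noise 2 cm |
|---|---|---|
| c = 22 cm (cohort mean) | about 5% | about 5% |
| c = 20 cm | 37% | 19% |
| c = 18 cm | 90% | 59% |

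A rejection in the lower rows says that there is a mean bias, not that it varies with depth.

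**4. What a regression on measured depth would detect in the same setting.**

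| True slope | Noise 1 cm | Noise 2 cm |
|---|---|---|
| -0.3 | 99% | 67% |
| -0.2 | 87% | 38% |
| -0.1 | 37% | 13% |

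**5. Precision.** The 95% CI half-width of the slope is about t(18) × SD of error / (SD of depth × √19). With t(18) = 2.10 and depth SD 4 cm this is 2.10 × 1 / (4 × 4.36) = 0.12 for error SD 1 cm, and 0.24 for 2 cm. Over depth SD 3 to 5 cm the range is 0.10 to 0.16 and 0.19 to 0.32.

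**6. Effect of reading error.** Measured depth enters both the difference and the horizontal axis. With no real slope, the expected slope is about -(reading SD)² / (depth SD² + reading SD²). For reading SD 1 cm this is -1/(16 + 1) = -0.06; for 0.5 cm it is -0.25/16.25 = -0.015.

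**7. Why centimetres.** A constant 1 cm offset is 1/14 = 7.1% at 14 cm and 1/30 = 3.3% at 30 cm. On the percentage scale a pure offset looks like a depth trend.

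**The case against.** Four arguments deserve weight.

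- *The planned outputs are not wholly blind to a trend.* With percentages on measured depth, the mean difference in cm minus (average percentage × mean measured depth) equals the covariance of percentage error with depth. In set A that is -0.28 - 0 = -0.28 cm; in set B it is 0.00 cm. A reader might infer that nothing planned could ever reveal a trend, and that is too strong. What stands is that this trace is indirect, has no confidence interval, depends on a denominator that 8.2 does not state, and is not an analysis that anyone is asked to do.
- *The purpose is optional.* Sections 2.1.2 and 2.2.2 say only that inaccuracy could be used; they promise neither a recalibration nor a description of the error's form. This stands and limits the weight of the point.
- *Nothing is lost by waiting.* Both depths will exist for every patient, so the plot could be added at analysis. This is true, but a prespecified look is worth more than an unplanned one and costs the same.
- *The example is extreme.* Set A is perfectly monotone, and the 5% rejection rate needs the error to cross zero at the cohort mean. With a crossing at 18 cm the t-test often rejects. This stands as far as signalling a need for adjustment goes, but the rejection still does not show the form of the error.

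**Conclusion.** The point holds as a gap in the planned analysis. Section 8.2 contains no direct check for depth-related error, and following it as written could leave such an error unrecognised or visible only as a mean bias. That the summaries ignore pairing with depth is a matter of arithmetic and needs no assumption. The detection rates and interval widths rest on assumed values and are illustrations.

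The weight is minor to moderate: worth changing because it is cheap. Two stronger readings are not supported. A reader might infer that the primary result is undermined; it is not, because the per-patient percentages with their extremes and the mean comparison still describe accuracy and serve the basis given in 8.1. A reader might also infer that a fitted slope would settle accuracy in children, since section 1.2 gives a paediatric use and section 4.2 admits only patients over 16. Applying such a slope to paediatric depths may be extrapolation.

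**What to change.** Add to section 8.2, as an exploratory analysis for the secondary objective:

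1. A plot of predicted minus measured depth, in cm, against measured depth.
2. A regression of that difference on measured depth centred at the cohort mean, reporting intercept and slope with 95% CIs as estimates. With this centring, the intercept is the mean bias and the slope is the change in error per cm of depth.
3. A statement that a non-significant slope is not proof of no slope, and that error in reading the measured depth biases the slope downward (about -0.06 for a reading-error SD of 1 cm and an assumed depth SD of 4 cm).

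A fit against the average of the two depths is not needed. It estimates a different quantity: with no noise a true slope b becomes b/(1 + b/2), so -0.3 becomes -0.353 and +0.3 becomes +0.261.

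The cost is one plot and one short regression, in software that 8.2 already names, on data already collected and with no extra patients. There are three downsides. The slope is imprecise at n=20 (half-width about 0.12 to 0.24 cm per cm under the assumptions above). Reading error can hide a real positive slope: with reading SD 1 cm, a true +0.3 averages +0.22 and is detected in 64% (noise 1 cm) or 36% (noise 2 cm) of runs. And a slope in the output does not by itself say which internal model value to change.

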## INTRODUCTION

### 1.1 BACKGROUND

Exposure to ionising radiation is understood to be associated with a small increase in the risk of developing cancer later in life. Therefore, all medical exposures need to be justified to ensure that the benefits from the exposure outweigh the risk, and optimised to ensure that the exposure is as low as reasonably practicable consistent with the intended purpose of the exposure.

Patient dose audit is an important part of the optimisation process. It gives information as to the level of dose received on average for an examination on one x-ray machine, allowing a comparison between multiple x-ray machines on the same site and between sites. For all commonly undertaken examinations, national reference levels exist; these are created from local data from all over the UK. Any institution is able to compare their local performance against these national values and determine if they are in line with average national performance or if urgent optimisation is required.

Whereas a patient dose audit for adult x-ray examinations requires only limited information relating to the exposure factors used and the amount of radiation measured by the equipment as delivered to the patient, the method for paediatric patient dose audit also requires a measurement of patient size to be made. This measurement should be either the anterior-posterior or lateral depth of the patient, depending on the examination projection.

Alternatively, a measurement of height and weight can be made, from which can be estimated the equivalent cylindrical diameter of the patient, which is equivalent to the measured depth.

National data collection exercises have revealed that these measurements are not being routinely made for paediatric patients undergoing x-ray examinations however. This has meant that no national reference levels have been proposed for paediatric x-rays since 2000. Since 2000, there have been significant technological improvements to the equipment used for x-ray imaging throughout the UK, so these reference values are out of date.

The lack of up to date reference values is affecting efforts to optimise paediatric x-ray exposures across the UK, despite this being the patient cohort for whom optimisation is most important.

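### Section 8.2 reports the model's percentage errors with no yardstick for the error obtained without the model, so the planned summaries may not show whether it carries information about individual patients

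*Combined protocol and SAP*

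**What the plan says.** Section 8.2 defines the outcome for each patient: "the difference between the computationally predicted AP abdomen depth and that measured for each individual participant will be expressed as a percentage". It then plans "Some statistical analyses will be undertaken on the 20 individual results (average, median, minimum and maximum deviations", and finally: "A t-test will be used to compare predicted and measured results". It does not say whether the average deviation is signed or absolute, or whether the t-test is paired. No reference predictor, correlation, limits of agreement or spread of measured depths is planned.

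Section 8.1 fixes 20 patients and says of that number: "There is no statistical aim or calculation in deriving this number". It ties confidence in the model to the case "where all or most results are found to be individually accurate", and puts no figure on either 'most' or 'accurate'.

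The only comparator anywhere is the physical depth measurement (2.1.1, 3.1). The decision that the pilot feeds is whether to take the model into further clinical investigation or to adjust it (3.1, 4.1).

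**The concern.** The model exists to supply an individual patient's size where nobody has measured it (1.1, 1.2). A percentage error can be read for that purpose only against the error one would make without the model. If depths vary little between patients, one value given to everybody already produces small percentage errors. If they vary a lot, it does not.

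The same average deviation from the model, say 8%, can therefore mean a useful individual estimate or nothing better than the group mean. Section 8.2 reports the deviation but neither the spread of depths nor the error of a simple guess, so a reader of the results could not tell which applies. What is at stake is a misreading of the decision to proceed or adjust.

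**Working it through.** **Inputs from the documents.** n = 20, each patient serving as their own reference (8.1, 8.2); deviation as a percentage (8.2), taken here as a percentage of measured depth; success described as all or most results accurate (8.1). The sample size of 20 cannot be reproduced, because 8.1 says no calculation lies behind it.

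**Assumptions, not in the documents.** Measured depth normal with mean 22 cm and SD 2, 3 or 4 cm (coefficient of variation 2/22 = 9%, 3/22 = 14%, 4/22 = 18%), floored at 10 cm. Tolerances of 5% to 20%. 'Most' read as 11 of 20 (simple majority) or 16 of 20 (80%).

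**Step 1: error of a guess that ignores the image.** For patient i with depth mᵢ, the guess is gᵢ = (S − mᵢ)/19, where S is the sum of all 20 depths. The deviation is |gᵢ − mᵢ|/mᵢ. Simulated sets of 20 (40,000 sets) give:

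| Assumed SD | Mean absolute deviation | Patients within 10% | Within 15% | Within 20% | Sets with at least 11 of 20 within 15% | Median largest deviation |
|---|---|---|---|---|---|---|
| 2 cm | 7.6% | 72% | 89% | 96% | 100% | 21% |
| 3 cm | 11.6% | 53% | 72% | 85% | 97% | 35% |
| 4 cm | 16% | 41% | 59% | 72% | 71% | 52% |

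**Step 2: dependence on the undefined terms.** At SD 3 cm:
- at least 11 of 20 within 15%: 97% of sets;
- at least 11 of 20 within 10%: 51%;
- at least 16 of 20 within 15%: 30% to 31% across runs.

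At SD 4 cm, at least 16 of 20 within 15% occurs in 4%. With a 5% tolerance, a simple majority occurs in 15%, 1% and 0.1% of sets for SD 2, 3 and 4 cm. The guess passes or fails according to figures the protocol does not set.

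**Step 3: the t-test.** The guesses sum to Σ(S − mᵢ)/19 = (20S − S)/19 = S, which is the sum of the measured depths. The mean difference in centimetres is therefore exactly zero in every sample, t = 0, and the test never rejects. A fixed constant equal to the population mean, rather than the sample mean, gives a non-significant paired test in about 94% to 95% of sets (depths lognormal, coefficient of variation 10% to 25%). An unbiased model gives about 95%. The test addresses mean bias only and cannot separate them.

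**Step 4: the minimum and maximum.** The median largest absolute deviation is about 11% for a model with 5% error SD and 21% for one with 10%. Against the last column of the table, the extremes separate the guess from a precise model, or from either model when depths are widely spread. At SD 2 cm the guess and the 10% model both give 21%.

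**Step 5: why the model's own figure is not enough.** With normal error of SD 10%, the model's mean absolute deviation is 10% × √(2/π) = 8.0%, whatever the spread of depths. At SD 2 cm (guess 7.6%) the model has the smaller mean absolute deviation in 41% of sets; at SD 4 cm (guess 16%), in over 99%. The reported average is the same and the conclusion is opposite.

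**Step 6: what 20 patients can support.** Power of a paired, two-sided 5% test that the model's absolute deviation is smaller than the guess's (4,000 sets, lognormal depths):

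| Model error SD | CV 10% | CV 15% | CV 20% | CV 25% |
|---|---|---|---|---|
| 5% | 75% | 98% | >99% | >99% |
| 10% | 3% | 37% | 75% | 92% |

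Power is low when model error is close to the natural spread, so the comparison should not be a pass/fail test.

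**The case against.** The strongest reply is that the stated objective (2.1.1, 2.2.1) is agreement with a physical measurement, not superiority over another predictor. Such a study needs a tolerance first, and the absence of a tolerance and of a meaning for 'most' is the deeper gap: a tight tolerance with a demanding 'most' would defeat the guess without any benchmark. This largely stands, and missing the benchmark does not stop the stated objective being met. But no tolerance is set, and a stated tolerance of 15% with a simple majority would still be met by guessing in 97% of sets at SD 3 cm. The decision to proceed or adjust still needs something to read the error against.

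A second reply is that the minimum and maximum would reveal a constant. They often would, but not always (step 4). A third is that the guess borrows the measured depths of the other patients, which an audit without measurements would not have, so it is a favourable version of guessing. That is fair: a constant far from the sample mean would show up as bias.

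Three stronger readings are tempting, and the documents do not support them:
- *The pilot cannot show that the model adds information.* The planned summaries may not show it, but the 20 predicted and measured pairs will exist and allow the comparison.
- *The patients will be of similar build, so any predictor looks good.* Section 4.2 admits any ambulatory patient over 16 attending for the examination who has no contrast media present, without restriction on build, and the spread of depths is not given.
- *A height-and-weight comparator is required.* Section 1.1 does say "Alternatively, a measurement of height and weight can be made, from which can be estimated the equivalent cylindrical diameter of the patient", but in describing paediatric dose audit. This study recruits patients over 16, 7.1 does not record height or weight, and 7.2 limits the form to what the study's aims, eligibility and safety need.

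**Conclusion.** The point holds in a limited form. Section 8.2 gives no yardstick for the error obtained without the model, and the t-test cannot supply one. Under the assumed depths, guessing the mean of the other 19 gives a mean absolute deviation of about 8%, 12% or 16% for SD 2, 3 or 4 cm. Whether that would count as accurate for most patients ranges from nearly certain to very unlikely, depending on a tolerance and a meaning of 'most' that 8.1 leaves open. The planned summaries may therefore fail to show whether the model carries individual information.

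Every magnitude here rests on assumed spreads, tolerances and model errors. The structural gap does not. It concerns interpretation and can be repaired from the data already planned; it does not undermine data collection.

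**What to change.** Add to 8.2, before any results are seen, wording to this effect: *As a reference, each patient will also be assigned the mean measured depth of the other 19 patients. The mean absolute percentage deviation of this reference and the SD of measured depth will be reported beside the mean absolute percentage deviation of the model. The within-patient difference in absolute percentage deviation will be given with a 95% confidence interval, as a description and not as a criterion of success.*

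This uses only data already collected and costs about one spreadsheet column, plus whatever approval 11.1 requires for a change to the protocol. The descriptive status matters: with 20 patients, an inconclusive interval must not be read as failure of the model. The addition complements, and does not replace, stating a tolerance and a number for 'most' in 8.1.

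A height-and-weight comparator is optional. It would need two more items on the study form and an amendment, and is not part of this fix.
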